**10.3. Tertiary endpoints****For Part A and Part B:**

- Cell-mediated immune response profile with respect to components of the investigational vaccine at pre-vaccination (Day 1), 30 days post-Dose 1 (Day 31), pre-Dose 2 (Day 61) and 30 days post-Dose 2 (Day 91):
  - Frequency of RSVPreF3-specific CD4+ and/or CD8+ T-cells identified as expressing one or any combination of immune marker(s) in vitro.

**For Part B only:**

- Humoral immune response with respect to components of the investigational vaccine at pre-vaccination (Day 1) and 30 days post-Dose 2 (Day 91):
  - Neutralizing antibody titers against RSV serotype B in all subjects.
  - RSVPreF3 **RSB1** specific antibody concentrations in a subset of subjects who received the selected vaccine formulation or placebo. **(Amended, 13 May 2020)**
- Cell-mediated immune response profile with respect to components of the investigational vaccine at pre-vaccination (Day 1), 30 days post-Dose 1 (Day 31) and 30 days post-Dose 2 (Day 91):
  - Frequency of RSVPreF3-specific memory B-cells in a subset of subjects who received the selected level of antigen dose (3 RSV vaccine formulations) or placebo.
- Persistence of the humoral immune response with respect to components of the investigational vaccine at Months 8 and 14:
  - Neutralizing antibody titers against RSV serotype A.
  - RSVPreF3-specific IgG antibody concentrations.

**CONFIDENTIAL**208851 (RSV OA=ADJ-002)  
Protocol Amendment 1 Final

- Persistence of the cell-mediated immune response profile with respect to components of the investigational vaccine:
  - Frequency of RSVPreF3-specific CD4+ and/or CD8+ T-cells identified as expressing one or any combination of immune marker(s) in vitro, in all subjects (Month 8) and in a subset of subjects who received the selected level of antigen dose (3 RSV vaccine formulations) or placebo (Month 14).
  - Frequency of RSVPreF3-specific CD4+ T-cells identified as expressing at least 2 markers among IL-2, CD40L, TNF- $\alpha$ , IFN- $\gamma$  in vitro, in all subjects (Month 8) and in a subset of subjects who received the selected level of antigen dose (3 RSV vaccine formulations) or placebo (Month 14).
  - Frequency of RSVPreF3-specific memory B-cells at Month 14 in a subset of subjects who received the selected level of antigen dose (3 RSV vaccine formulations) or placebo.
- Any further exploratory immunology to detect RSV-related immune responses, such as but not limited to:
  - Antibodies against specific protein F epitopes.
  - Potential new immunological markers for protection.
  - Cross-reactive neutralizing antibody titers against hMPV.
- Occurrence of RSV-associated RTI, including co-infections with other respiratory viruses (as measured by multiplex PCR in self-collected nasal swab samples and nasal/throat swab samples collected during the assessment visit for potential RSV-RTI) during the RSV seasons.
- Occurrence of RSV-associated RTI as measured by qRT-PCR in self-collected nasal swab samples during the RSV seasons, up to the end of follow-up.

#### **10.4. Determination of sample size**

In Part A, the sample size of 12 subjects per group would provide a probability of 80% or 90% to observe at least one AE, if the true AE rate is 12.6% or 17.5%, respectively.

In Part B, the sample size of 100 subjects per group would provide a probability of 80% or 90% to observe at least one AE, if the true AE rate is 1.6% or 2.3%, respectively.

The study is designed as a factorial design with 2 factors resulting in 9 RSV formulations (~100 subjects per RSV formulation in Part B, Step 1 and Step 2 pooled, referred as “group” in text below) (see [Table 31](#)). In addition, a placebo group will be evaluated (~100 subjects, Step 1 and Step 2 pooled).

**CONFIDENTIAL**208851 (RSV OA=ADJ-002)  
Protocol Amendment 1 Final**Table 31 Factorial design**

		No adjuvant (Plain)	Factor B: Adjuvant	
			AS01 E	AS01 B
Factor A: Antigen dose	30 µg	100	100	100
	60 µg	100	100	100
	120 µg	100	100	100

Considering a 10% rate of non-evaluable subjects, it is assumed that approximately 90 subjects per group will be evaluable for the analysis of RSV-A neutralizing antibody titers and for the CD4+ T-cells response.

The 9 RSV formulations will be first compared to the Placebo in terms of RSV-A neutralizing antibody titers at Day 91 using the Dunnett's method via a one way ANOVA model. The sample size of 90 subjects per group (in 10 groups) achieves  $\geq 90\%$  power to detect a difference of at least 2.3-fold (alpha=0.025, SD=0.4, CV=115.6%, PASS 12.0.10 Multiple comparisons Analysis using Dunnett's adjustment for multiplicity).

The effect of the second vaccination will then be evaluated by comparing the response one month post-Dose 2 (Day 91) and one month post-Dose 1 (Day 31) in terms of RSVPreF3-specific CD4+ T-cells and RSV-A neutralizing antibodies. This comparison will be done on the groups pooled according to their adjuvant content (3 groups of 270 subjects: AS01B, AS01E and Plain). [Table 32](#) below presents the power and fold increase that can be detected with a sample size of 270 subjects per pooled group. The sample size of 270 subjects per group achieves 90% power to detect a difference of at least 1.2 fold between Dose 2 and Dose 1.

**Table 32 Effect of second vaccination: Power and fold increase with a sample size of 270 subjects per pooled group**

N/group	N evaluable/group	N Pooled groups	Power	Fold increase
100	90	270	90%	1.2
			80%	1.17

Power calculation done in PASS 12.0.10: Paired T-test with alpha=0.025, SD=0.4 (CV=115.6%).

The effect of the adjuvant will also be evaluated on the same pooled groups (according to adjuvant content: AS01B, AS01E, Plain) by comparing sequentially the 2 adjuvanted groups to the Plain group, in terms of RSVPreF3-specific CD4+ T-cells and RSV-A neutralizing antibody titers at Day 91. [Table 33](#) below presents the power and fold increase that can be detected with a sample size of 270 subjects per pooled group. The sample size of 270 subjects per group achieves 90% power to detect a difference of at least 1.3-fold between one adjuvanted group and the Plain group.

**Table 33 Effect of adjuvant: Power and fold increase with a sample size of 270 subjects per pooled group**

N/group	N evaluable/group	N Pooled groups	Power	Fold increase
100	90	270	90%	1.3
			80%	1.25

Power calculation done in PASS 12.0.10: Two-sample T-test assuming equal variance, with alpha=0.025, SD=0.4 (CV=115.6%).

**CONFIDENTIAL**208851 (RSV OA=ADJ-002)  
Protocol Amendment 1 Final

Finally, the antigen dose-response will be evaluated in each adjuvanted group in terms of RSV-A neutralizing antibody titers and RSVPreF3-specific CD4+ T-cells at Day 91.

**Table 34** below presents the power and fold increase that can be detected with a sample size of 90 per group. The sample size of 90 subjects per group would provide 90% power to detect a difference of at least 1.56 between 2 groups.

**Table 34 Antigen dose-response: Power and fold increase with a sample size of 90 subjects per group**

N/group	N evaluable/group	Power	Fold increase
100	90	90%	1.56
		85%	1.51
		80%	1.47

Power calculation done in PASS 12.0.10: Two-sample T-test assuming equal variance, with alpha=0.025, SD=0.4 (CV=115.6%).

## 10.5. Cohorts for Analyses

### 10.5.1. Exposed Set

The Exposed Set (ES) will include all subjects with study vaccine administration documented.

A safety analysis based on the ES will include all vaccinated subjects.

An immunogenicity analysis based on ES will include all vaccinated subjects for whom immunogenicity data are available.

The ES analysis will be performed per treatment actually administered.

### 10.5.2. Per-protocol Set for analysis of immunogenicity

The Per Protocol set (PPS) for analysis of immunogenicity will be defined by time point (to include all eligible subjects' data up to the time of important protocol deviations). The PPS will include all evaluable subjects in the ES:

- Meeting all eligibility criteria.
- For whom the administration route of the vaccine was as according to protocol.
- For whom the study vaccine was administered as per protocol.
- Who did not receive a concomitant medication/ product leading to exclusion from a PP analysis, as described in Section 6.6.2, up to the considered time point.
- Who did not present with a medical condition leading to exclusion from a PP analysis, as described in Section 6.7, up to the considered time point.
- Who complied with the vaccination schedule, as specified in [Table 8](#).
- Who complied with the timings of the post-vaccination blood sampling for immune response evaluation, as specified in [Table 8](#).

**CONFIDENTIAL**208851 (RSV OA=ADJ-002)  
Protocol Amendment 1 Final

- For whom post-vaccination immunogenicity results are available for at least one assay component at the corresponding time points.

## 10.6. Derived and transformed data

### Demography

- For a given subject and a given demographic variable, missing measurements will not be replaced.

### Safety

- For a given subject and the analysis of solicited symptoms during the 7-day follow-up period after vaccination, missing or non-evaluatable measurements will not be replaced. Therefore, the analysis of the solicited symptoms based on the ES will include only vaccinated subjects with documented safety data (i.e., eDiary completed).
- For analysis of unsolicited AEs, SAEs, pIMDs, pregnancies and concomitant medications, all vaccinated subjects will be considered. Subjects who did not report an event or concomitant medication will be considered as subjects without the event or the concomitant medication respectively.

### Immunogenicity

- Any missing or non-evaluatable immunogenicity measurement will not be replaced:
  - For the within-group assessment, the descriptive analysis performed for each assay at each time point will exclude subjects with a missing or non-evaluatable measurement. Kinetics will be plotted on subjects with results available at all time points.
  - For the between group assessments, the Analysis of covariance (ANCOVA) model will be fitted based on the subjects having a result at both the baseline and the considered time point.
- The geometric mean titers (GMTs)/geometric mean concentrations (GMCs) will be computed by taking the anti-logarithm of the arithmetic mean of the  $\log_{10}$  transformed titers/concentrations.
- A seronegative subject will be defined as a subject whose antibody titer/concentration is below the cut-off value of the assay. A seropositive subject is a subject whose antibody titer/concentration is greater than or equal to the cut-off value of the assay.
- The description of the handling of data below the lower limit of quantification for GMT/GMC calculation and fold increase will be described in the SAP.

**CONFIDENTIAL**208851 (RSV OA=ADJ-002)  
Protocol Amendment 1 Final

## 10.7. Analysis of demographics

Demographic characteristics (age at vaccination in years, gender, race and ethnicity) will be summarized by group using descriptive statistics:

- Frequency tables will be generated for categorical variable such as race.
- Mean, median, standard error and range will be provided for continuous data such as age.

The distribution of subjects will be tabulated as a whole and per group and for each age category (60-69 years and 70-80 years in Part B only).

Withdrawal status will be summarized by group using descriptive statistics:

- The number of subjects enrolled into the study as well as the number of subjects excluded from PP analyses will be tabulated.
- The numbers of withdrawn subjects will be tabulated according to the reason for withdrawal.

## 10.8. Analysis of safety

The percentage of subjects with at least one local AE (solicited and unsolicited), with at least one general AE (solicited and unsolicited) and with any AE during the 7-day or 30-day follow-up period will be tabulated with exact 95% confidence interval (CI) after each dose and overall. The same computations will be done for Grade 3 AEs, for any AEs considered related to vaccination, for Grade 3 AEs considered related to vaccination and for Grade 3 non-serious AEs.

The percentage of subjects with any AE (solicited and unsolicited) resulting in a medically attended visit during the 30-day follow-up period will also be tabulated after each dose and overall.

The percentage of subjects reporting each individual solicited local AE (any grade and Grade 3) and solicited general AE (any grade, Grade 3, any related and Grade 3 related) during the 7-day follow-up period (i.e., on the day of vaccination and 6 subsequent days) will be tabulated for each group after each dose and overall.

For fever, the number and percentage of subjects reporting fever by half degree (°C) cumulative increments during the 7-day follow-up period (i.e., on the day of vaccination and 6 subsequent days) will be tabulated for each group after each dose and overall. Similar tabulations will be performed for any fever with a causal relationship to vaccination and for Grade 3 ( $> 39.0^{\circ}\text{C}/102.2^{\circ}\text{F}$ ) causally related fever. In addition, the prevalence of any and Grade 3 fever will be presented graphically over time after each vaccination.

**CONFIDENTIAL**208851 (RSV OA=ADJ-002)  
Protocol Amendment 1 Final

For each group and for each hematology and biochemistry parameter:

- The percentage of subjects having hematology and biochemistry results below or above the laboratory normal ranges will be tabulated by time point.
- The summary of grading post-vaccination will be tabulated versus baseline. (Grades will be based on the FDA Guidance for Industry “Toxicity Grading Scale for Healthy Adults and Adolescent Volunteers Enrolled in Preventive Vaccine Clinical Trials”, see [APPENDIX C](#). Those laboratory parameters not included on FDA Toxicity Grading Scale will not be graded).

The percentage of subjects with any unsolicited AEs during the 30-day follow-up period (i.e., on the day of vaccination and 29 subsequent days) with its exact 95% CI will be tabulated by group and by Medical Dictionary for Regulatory Activities (MedDRA) preferred term. Similar tabulation will be done for Grade 3 unsolicited AEs, for any causally related unsolicited AEs, for Grade 3 causally related unsolicited AEs and for unsolicited AEs resulting in a medically attended visit. The verbatim reports of unsolicited AEs will be reviewed by a physician and the signs and symptoms will be coded according to the MedDRA Dictionary for Adverse Reaction Terminology. Every verbatim term will be matched with the appropriate Preferred Term.

The percentage of subjects with at least one report of SAE classified by the MedDRA Preferred Terms and reported during the entire study period will be tabulated with exact 95% CI. SAEs will also be described in details.

For Part A only, pregnancy and pregnancy outcomes will be listed (if applicable).

For Part B only, the percentage of subjects with at least one pIMD classified by the MedDRA Preferred Terms and reported during the entire study period will be tabulated with exact 95% CI. PIMDs will also be described in details.

The percentage of subjects using concomitant medication (any medication, any antipyretic and any antipyretic taken prophylactically, respectively) during the 7-day follow-up period (i.e., on the day of vaccination and 6 subsequent days) and during the 30-day follow-up period (i.e., on the day of vaccination and 29 subsequent days) will be summarized by group after each vaccine dose and overall.

The analysis of safety will also be performed by age category (60-69 years and 70-80 years in Part B only).

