- Any other condition (e.g. chronic obstructive pulmonary disease or severe respiratory condition) that, in the opinion of the investigator, might interfere with the evaluations required by the study.
- History of any neurological disorders or seizures.
- Acute disease and/or fever at the time of enrolment.
  - Fever is defined as temperature  $\geq 38.0^{\circ}\text{C} / 100.4^{\circ}\text{F}$ . The preferred location for measuring temperature in this study will be the oral cavity.
  - Subjects with a minor illness (such as mild diarrhoea, mild upper respiratory infection) without fever may be enrolled at the discretion of the investigator.

For subjects with acute disease and/or fever at the time of enrolment/vaccination, Visit 1 may be re-scheduled within the allowed time-window.
- Acute or chronic, clinically significant pulmonary, cardiovascular, hepatic or renal functional abnormality, as determined by the investigator based on medical history, physical examination or laboratory screening tests.
- Hepatomegaly, right upper quadrant abdominal pain or tenderness.
- Administration of immunoglobulins and/or any blood products during the period starting 3 months before the first dose of study vaccine or planned administration during the study period.
- History of chronic alcohol consumption and/or drug abuse as deemed by the investigator to render the potential subject unable/unlikely to provide accurate safety reports.
- Significant underlying illness that in the opinion of the investigator would be expected to prevent completion of the study (e.g., life-threatening disease likely to limit survival to less than 2 years).
- Previous vaccination with an RSV vaccine.
- Lymphoproliferative disorder and malignancy within 5 years.
- Body mass index  $> 40 \text{ kg/m}^2$ .
- Planned move to a location that will prohibit participating in the trial until study end.
- At screening: Hematology parameters (complete blood cell count [red blood cells, white blood cells], white blood cells differential count [lymphocytes, neutrophils and eosinophils], platelets count or hemoglobin level) and/or biochemistry parameters (creatinine, blood urea nitrogen or liver enzymes [alanine aminotransferase [ALT] or aspartate aminotransferase [AST]]) outside the normal laboratory ranges, unless the laboratory abnormalities are considered not clinically significant by the investigator.

**CONFIDENTIAL**208851 (RSV OA=ADJ-002)  

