**Table 12 Hematology/biochemistry**

System	Discipline	Component	Method	Scale**	Laboratory
Whole blood	Hematology	Leukocytes (White Blood Cells)	As per central laboratory procedure	Quantitative	Q  Solutions
		Neutrophils*			
		Lymphocytes*			
		Basophils*			
		Monocytes*			
		Eosinophils*			
		Hemoglobin			
		Platelets			
		Erythrocytes (Red Blood Cells)			
Serum	Biochemistry	Alanine Aminotransferase (ALT)			
		Aspartate Aminotransferase (AST)			
		Creatinine			
		Blood Urea Nitrogen (BUN)			
		Uric Acid			

\*For White Blood Cell (WBC) differential count.

\*\*Grading of laboratory parameters will be based on the Food and Drug Administration (FDA) Guidance for Industry

“Toxicity Grading Scale for Healthy Adult and Adolescent Volunteers Enrolled in Preventive Vaccine Clinical Trials” (refer to [APPENDIX C](#)). Basophils, monocytes, erythrocytes and uric acid are not included in the FDA Toxicity Grading Scale and will not be graded.

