\*\*\* At Visit 8, blood samples for antibody and CMI determination will be collected and tested from all subjects in part B1; and from a subset of subjects in part B2, who received a selected level of antigen dose and Placebo.

**CONFIDENTIAL**208851 (RSV OA=ADJ-002)  
Protocol Amendment 1 Final**5.9.4.2. Haematology/Blood Chemistry and CMV serology****Table 16 Hematology and biochemistry read-outs and CMV serology testing**

Blood sampling time point		Sub-cohort	No. subjects	Component
Type of contact and time point	Sampling time point			
Part A				
screening visit*	Pre-Day 1	All screened subjects	≥ 48	Hematology: leukocytes, neutrophils, lymphocytes, basophils, monocytes, eosinophils, hemoglobin, platelets, erythrocytes Biochemistry: ALT, AST, creatinine, BUN, uric acid
visit 1 (Day 1) visit 2 (Day 8) visit 4 (Day 61) visit 5 (Day 68)	Pre-Vacc PI D8 PI D61 PII D68	All enrolled subjects	~ 48	
visit 1 (Day 1)	Pre-Vacc	All enrolled subjects	~ 48	Anti-CMV IgG antibody
Part B				
screening visit*	Pre-Day 1	All screened subjects	≥ 48	Hematology: leukocytes, neutrophils, lymphocytes, basophils, monocytes, eosinophils, hemoglobin, platelets, erythrocytes Biochemistry: ALT, AST, creatinine, BUN, uric acid
visit 1 (Day 1) visit 2 (Day 8) visit 4 (Day 61) visit 5 (Day 68)	Pre-Vacc PI D8 PI D61 PII D68	All enrolled subjects	~ 1000	
visit 1 (Day 1)	Pre-Vacc	All enrolled subjects	~ 1000	Anti-CMV IgG antibody

Pre-Vacc: Pre-vaccination; PI DX: Post-Dose 1 Study Day X; PII DX: Post-Dose 2 Study Day X

ALT = Alanine Aminotransferase; AST = Aspartate Aminotransferase; BUN = Blood Urea Nitrogen

CMV = Cytomegalovirus

\* In case Visit 1 occurs more than 30 days after the Screening Visit, a re-screening visit should be scheduled before Visit 1 during which blood sample collection for safety laboratory assessment must be repeated (maximum one re-screening per subject is allowed). Only laboratory results from the re-screening visit, if it occurs, will be taken into consideration and recorded in the eCRF. Medical history, physical examination and review of inclusion/exclusion criteria must be repeated if a re-screening visit occurs. The subject can only be randomized once the investigator receives the results and confirms the eligibility criteria.

CONFIDENTIAL

208851 (RSV OA=ADJ-002)  
Protocol Amendment 1 Final**5.9.4.3. Molecular biology****Table 17 Molecular biology tests on nasal/throat swab specimen for Part B**

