### 10.1. Primary endpoints

#### For Part A and Part B:

- Occurrence of AEs from first vaccination up to 30 days after the second vaccination (Day 91):
  - Occurrence of each solicited local and general AE during a 7-day follow-up period (i.e., on the day of vaccination and 6 subsequent days) after each vaccination.
  - Occurrence of any unsolicited AE during a 30-day follow up period (i.e., on the day of vaccination and 29 subsequent days) after each vaccination.
  - Occurrence of any hematological (erythrocytes, WBC and differential count, platelets count and hemoglobin level) and biochemical (ALT, AST, creatinine, BUN and uric acid) laboratory abnormalities at Days 1, 8, 61 and 68.
  - Occurrence of all Grade 3 non-serious AEs (solicited and unsolicited) during the 30-day follow-up period after each vaccination.
  - Occurrence of SAEs from Dose 1 up to 30 days after the second vaccine dose (Day 91).

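### The primary laboratory endpoint counts pre-vaccination Day 1 values as outcomes, and ungraded parameters get no within-subject comparison with baseline

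*Protocol*

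**What the plan says.** Section 10.1 of the protocol, repeated in the synopsis, heads the primary endpoint "Occurrence of AEs from first vaccination up to 30 days after the second vaccination (Day 91"). One component beneath that heading is haematological and biochemical "laboratory abnormalities at Days 1, 8, 61 and 68". It names erythrocytes, the white-cell differential and uric acid among the parameters.

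Table 16 (section 5.9.4.2) labels the four post-screening samples, in visit order, "Pre-Vacc PI D8 PI D61 PII D68". Day 1 is therefore a pre-vaccination draw.

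Section 10.8 plans two laboratory outputs for each group and parameter:

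- The first is on out-of-range results: "The percentage of subjects having hematology and biochemistry results below or above the laboratory normal ranges will be tabulated by time point". No baseline category is mentioned.
- The second is on toxicity grades: "The summary of grading post-vaccination will be tabulated versus baseline". On the scope of this second output it adds: "Those laboratory parameters not included on FDA Toxicity Grading Scale will not be graded".

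The footnote to Table 12 identifies the parameters left out: "Basophils, monocytes, erythrocytes and uric acid are not included in the FDA Toxicity Grading Scale and will not be graded". Table 37 in Appendix C grades neutrophils, lymphocytes and platelets for decreases only.

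Under section 4.3, screening results exclude a subject if they are "outside the normal laboratory ranges, unless the laboratory abnormalities are considered not clinically significant by the investigator". The parameters listed in that criterion do not include uric acid, basophils or monocytes.

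**The concern.** A value measured before the first dose cannot be an outcome of vaccination, yet the endpoint wording makes it one and so conflicts with the heading above it. This is fixed in the primary endpoint definition, so any analysis plan built on it inherits the conflict.

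The second part concerns what the planned tables can show. Section 10.8 recognises that baseline matters, because it sets grades against baseline, but the out-of-range output has no such step. A subject whose uric acid is high at Day 1 and stays high is counted again at Days 8, 61 and 68, in the same cell as a subject whose uric acid became high after a dose. The entry criteria let such subjects in, and Part B enrols people aged 60 to 80 with stable chronic illness permitted, so persisting abnormalities are to be expected. For an antigen not previously given to humans, the question of interest is how many subjects became abnormal after vaccination.

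**Working it through.** The protocol states no figure on this point, so there is none to reproduce. The check is a reading of the passages followed by an illustration.

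**1. Timing.** The endpoint window opens at first vaccination (10.1). The Day 1 sample is taken before vaccination (Table 16). Of the four listed time points, Day 1 lies outside the window and Days 8, 61 and 68 lie inside it.

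**2. Coverage of the baseline comparison.** Table 12 lists 9 haematology and 5 biochemistry parameters, 14 in all. Four are ungraded, and 14 − 4 = 10 are graded: leukocytes, neutrophils, lymphocytes, eosinophils, haemoglobin, platelets, ALT, AST, creatinine and BUN.

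| Parameter or direction | Out-of-range % by visit | Grade versus baseline |
|---|---|---|
| Ten graded parameters, graded direction | yes | yes |
| Erythrocytes, uric acid, basophils, monocytes | yes | no |
| Rises in neutrophils, lymphocytes, platelets | yes | no |

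**3. What percentages by visit cannot show.** Take 100 subjects with 10 out of range at Day 1 and 10 at Day 8. If the same 10 are abnormal at both visits, there are 0 new abnormalities. If the first 10 all normalised, there are 10. The two columns are identical in either case; only a cross-classification within subjects separates them.

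**4. Size, on assumed rates.** None of these inputs is in the documents. Let a share p of subjects lie beyond one limit at each visit, and let Day 1 and Day 8 values be bivariate normal with correlation ρ. The share of Day 8 abnormals already abnormal on the same side at Day 1 is

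P(both visits beyond the limit) ÷ p.

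| p (one side) | ρ = 0.7 | ρ = 0.8 | ρ = 0.9 |
|---|---|---|---|
| 2.5% (z = 1.96) | 0.0083/0.025 = 33% | 0.0110/0.025 = 44% | 0.0148/0.025 = 59% |
| 15% (z = 1.04) | 0.0782/0.15 = 52% | 0.0913/0.15 = 61% | 0.1084/0.15 = 72% |

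The 2.5% row is what a central 95% normal range implies on each side. The 15% row represents a parameter that is often out of range in older adults.

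A simpler model points the same way. Suppose 10% are out of range at Day 1, 80% of those persist, and 5% of initially normal subjects become abnormal. Day 8 then shows 10 × 0.80 + 90 × 0.05 = 8.0 + 4.5 = 12.5 per 100, of which 8.0/12.5 = 64% were already abnormal. Varying the three inputs over 5-20%, 50-100% and 2-10% moves that share from 21% to 93%.

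**The case against.** The strongest reply is that the protocol already does most of what is needed.

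- Day 1 is its own column in the by-visit table, so baseline percentages sit beside later ones for every parameter.
- A randomised placebo group is tabulated alongside (1.2.2.5). Persisting abnormalities should balance on average.
- Ten of the 14 parameters have a grade-versus-baseline table, and rises in total leukocytes are graded even though rises in neutrophils and lymphocytes are not.
- Section 7.1.4 makes clinically significant laboratory worsening from baseline reportable as an adverse event, for any parameter.
- The layout of a shift table is commonly left to the statistical analysis plan, which is not at hand.

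Most of this stands, and it rules out stronger readings. A reader might infer that the ungraded parameters have no baseline comparison at all. They do have one at group level; what is missing is the comparison within subjects. A reader might also infer that Day 1 abnormalities are pooled into a post-vaccination rate and dilute it. Nothing in the protocol pools visits; a Day 1 abnormality affects the Day 8 percentage only if it persists. Nor can a loss of power be claimed, because section 10.8 plans no laboratory test and section 10.11 calls the analyses descriptive.

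Two things are not answered. Columns of percentages with a placebo arm still do not identify new abnormalities, and the adverse-event route depends on the investigator's view of clinical significance, whereas the endpoint counts any abnormality. Nor is the Day 1 wording a layout matter: it is in the protocol's primary endpoint. On the tables, the protocol does more than stay silent, since it fixes one output by time point and confines the baseline comparison to grades.

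**Conclusion.** The point holds in a limited form. The primary laboratory endpoint lists a pre-vaccination sample as an outcome time point, against its own heading. Section 10.8 leaves four parameters, and rises in three others, without a within-subject comparison with baseline, so new and persisting abnormalities cannot be separated in the outputs the protocol describes.

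How much this matters depends on how common and how stable out-of-range values are in this population, which the documents do not say. The illustrative pre-existing shares (33-59% at 2.5% per side, 52-72% at 15%) rest on assumed prevalence, bivariate normality and correlations of 0.7 to 0.9. They show that the share could be large, not what it will be.

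This does not undermine the safety evaluation: the graded parameters, the placebo comparison and adverse-event reporting remain. It is an inconsistency in a primary endpoint and a weaker table than the collected data allow, both correctable at almost no cost.

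**What to change.** - **Section 10.1 and synopsis:** name Day 1 as the baseline and define the laboratory outcome as abnormalities at Days 8, 61 and 68 relative to Day 1. Keep Day 1 percentages as a baseline description.
- **Section 10.8:** extend the comparison with baseline from grades to normal-range status. Tabulate below, within or above range at each of Days 8, 61 and 68 by Day 1 category, for each group. Do this at least for erythrocytes, uric acid, basophils and monocytes, and for the ungraded directions of graded parameters. One layout for all 14 would be simpler.
- **Optional:** also refer Day 68 to Day 61, the sample at the second-dose visit. The point does not depend on it.

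The cost is endpoint wording, matching text in the statistical analysis plan and one table layout. Tables 9 and 16 already require these samples from every enrolled subject, so no extra blood draw, visit or assay is needed.
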